12.4 List of Excluded Concomitant Medications

Treatments with concomitant drugs that are strong inhibitors or inducers of CYP3A4 are prohibited, including ketoconazole, high dose ritonavir, rifampin/rifampicin, carbamazepine and St. John's Wort or long acting barbiturates (e.g., phenytoin). Concomitant use of sirolimus, atorvastatin, cyclosporine, tacrolimus, midazolam, bupropion, mycophenolate mofetil and digoxin should be made with caution.

Treatments with concurrent drugs that are CYP3A4 substrates and have a narrow therapeutic range (e.g., vincristine) should be used with caution, and if clinically warranted, consider reduction of substrate dose. Use of other systemic antifungals is prohibited during study drug administration.

12.5 Liver Safety Monitoring and Assessment

Any subject enrolled in a clinical study with active drug therapy and reveals an increase of serum aminotransferases (AT) to $> 3 \times \text{ULN}$ or bilirubin $> 2 \times \text{ULN}$ should undergo detailed testing for liver enzymes (including at least ALT, AST, alkaline phosphatase [ALP] and TBL). Testing should be repeated within 72 hours of notification of the test results. For studies for which a central laboratory is used, alerts will be generated by the central laboratory regarding moderate and severe liver abnormality to inform the investigator and study team. Subjects should be asked if they have any symptoms suggestive of hepatobiliary dysfunction.

Definition of Liver Abnormalities

Confirmed abnormalities will be characterized as moderate and severe where ULN:

	ALT or AST		TBL
Moderate	$> 3 \times \text{ULN}$	or	$> 2 \times \text{ULN}$
Severe	$> 3 \times \text{ULN}$	and	$> 2 \times \text{ULN}$

In addition, the subject should be considered to have severe hepatic abnormalities for any of the following:

- ALT or AST $> 8 \times \text{ULN}$.
- ALT or AST $> 5 \times \text{ULN}$ for more than 2 weeks.
- ALT or AST $> 3 \times \text{ULN}$ and International Normalized Ratio (INR) > 1.5 (If INR testing is applicable/evaluated).
- ALT or AST $> 3 \times \text{ULN}$ with the appearance of fatigue, nausea, vomiting, right upper quadrant pain or tenderness, fever, rash and/or eosinophilia ($> 5\%$).

The investigator may determine that abnormal liver function results, other than as described above, may qualify as moderate or severe abnormalities and require additional monitoring and follow-up.

Follow-up Procedures

Confirmed moderate and severe abnormalities in hepatic functions should be thoroughly characterized by obtaining appropriate expert consultations, detailed pertinent history, physical examination and laboratory tests. The site staff is to complete the liver abnormality case report form (LA-CRF). Subjects with confirmed abnormal liver function tests (LFTs) should be followed as described below.

Confirmed moderately abnormal LFTs should be repeated 2 to 3 times weekly then weekly or less if abnormalities stabilize or the study drug has been discontinued and the subject is asymptomatic.

Severe hepatic liver function abnormalities as defined above, in the absence of another etiology, may be considered an important medical event and may be reported as a SAE. The sponsor should be contacted and informed of all subjects for whom severe hepatic liver function abnormalities possibly attributable to study drug are observed.

To further assess abnormal hepatic laboratory findings, the investigator is expected to:

- Obtain a more detailed history of symptoms and prior or concurrent diseases. Symptoms and new-onset diseases is to be recorded as “AEs” within the eCRF. Illnesses and conditions such as hypotensive events, and decompensated cardiac disease that may lead to secondary liver abnormalities should be noted. Nonalcoholic steatohepatitis is seen in obese hyperlipoproteinemic and/or diabetic subjects, and may be associated with fluctuating AT levels. The investigator should ensure that the medical history form captures any illness that predates study enrollment that may be relevant in assessing hepatic function.
- Obtain a history of concomitant drug use (including nonprescription medication, complementary and alternative medications), alcohol use, recreational drug use and special diets. Medications, is to be entered in the eCRF. Information on alcohol, other substance use and diet should be entered on the LA-CRF or an appropriate document.
- Obtain a history of exposure to environmental chemical agents.
- Based on the subject’s history, other testing may be appropriate including:
 - Acute viral hepatitis (A, B, C, D, E or other infectious agents),
 - Ultrasound or other imaging to assess biliary tract disease,
 - Other laboratory tests including INR, direct bilirubin.
- Consider gastroenterology or hepatology consultations.
- Submit results for any additional testing and possible etiology on the LA-CRF or an appropriate document.

Study Treatment Discontinuation

In the absence of an explanation for increased LFT’s, such as viral hepatitis, preexisting or acute liver disease or exposure to other agents associated with liver injury, the subject may be discontinued from study treatment. The investigator may determine that it is not in the subject’s best interest to continue study treatment. Discontinuation of study treatment should be considered if:

- ALT or AST $> 8 \times$ ULN.
- ALT or AST $> 5 \times$ ULN for more than 2 weeks.
- ALT or AST $> 3 \times$ ULN and (TBL $> 2 \times$ ULN or INR > 1.5) (If INR testing is applicable/evaluated).
- ALT or AST $> 3 \times$ ULN with the appearance of fatigue, nausea, vomiting, right upper quadrant pain or tenderness, fever, rash and/or eosinophilia ($> 5\%$).

In addition, if close monitoring for a subject with moderate or severe hepatic laboratory tests is not possible, study treatment should be discontinued.

*Hy’s Law Definition: Drug-induced jaundice caused by hepatocellular injury, without a significant obstructive component, has a high rate of bad outcomes, from 10 to 50% mortality (or transplant).

The 2 “requirements” for Hy’s Law are:

1. Evidence that a drug can cause hepatocellular-type injury, generally shown by an increase in transaminase elevations higher $3 \times \text{ULN}$ ($2 \times \text{ULN}$ elevations are too common in treated and untreated subjects to be discriminating).
2. Cases of increased bilirubin (at least $2 \times \text{ULN}$) with concurrent transaminase elevations at least $3 \times \text{ULN}$ and no evidence of intra- or extra-hepatic bilirubin obstruction (elevated ALP) or Gilbert’s syndrome [Temple, 2006].

FDA Guidance for Industry titled “Drug-Induced Liver Injury: Premarketing Clinical Evaluation” issued on July 2009:

1. The drug causes hepatocellular injury, generally shown by a higher incidence of 3-fold or greater elevations above the ULN of ALT or AST than the (nonhepatotoxic) control drug or placebo.
2. Among trial subjects showing such AT elevations, often with ATs much greater than $3 \times \text{ULN}$, one or more also show elevation of serum TBL to $> 2 \times \text{ULN}$, without initial findings of cholestasis (elevated serum ALP).
3. No other reason can be found to explain the combination of increased AT and TBL, such as viral hepatitis A, B or C; preexisting or acute liver disease; or another drug capable of causing the observed injury. [Guidance for Industry titled “Drug-Induced Liver Injury: Premarketing Clinical Evaluation” issued by FDA on July 2009]

References

Temple R. Hy’s law: Predicting Serious Hepatotoxicity. *Pharmacoepidemiol Drug Saf.* 2006;15(Suppl 4):241-3.

Guidance for Industry titled “Drug-Induced Liver Injury: Premarketing Clinical Evaluation” issued by FDA on July 2009.

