5.5.1.2 Potential Cases of Drug-Induced Liver Injury

Refer to [Appendix 12.5 Liver Safety Monitoring and Assessment] for detailed instructions on drug induced liver injury. Abnormal values in AST and/or ALT concurrent or with abnormal elevations in TBL that meet the criteria outlined in [Appendix 12.5 Liver Safety Monitoring and Assessment], in the absence of other causes of liver injury, are considered potential cases of drug-induced liver injury (including potential Hy's Law cases) and are always to be considered important medical events and reported per [Section 5.5.5 Reporting of Serious Adverse Events].

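### For combined ALT/AST and bilirubin elevations with no other cause, Protocol Section 5.5.1.2 makes SAE reporting mandatory while Appendix 12.5 makes it optional

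*Protocol*

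**What the plan says.** Protocol Section 5.5.1.2 defines the cases it covers as "Abnormal values in AST and/or ALT concurrent or with abnormal elevations in TBL that meet the criteria outlined in" Appendix 12.5, subject to the condition "in the absence of other causes of liver injury". It names potential Hy's Law cases as included. Such cases "are always to be considered important medical events and reported per" Section 5.5.5, which requires the investigator to contact the sponsor within 24 hours of awareness. For detailed instructions the section refers sites to Appendix 12.5.

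Appendix 12.5 classes a confirmed abnormality as severe when ALT or AST exceeds 3×ULN and total bilirubin (TBL) exceeds 2×ULN. It then widens the class: "In addition, the subject should be considered to have severe hepatic abnormalities for any of the following", followed by four criteria that need no bilirubin rise. Of severe abnormalities as a whole it says that, where there is no other etiology, they "may be considered an important medical event and may be reported as a SAE". The next sentence adds: "The sponsor should be contacted and informed of all subjects for whom severe hepatic liver function abnormalities possibly attributable to study drug are observed". Site staff are also to complete a liver abnormality case report form (LA-CRF) for confirmed moderate and severe cases.

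**The concern.** Both passages set the same condition (no alternative cause) and concern the same action (important medical event, SAE report). One obliges and the other permits, and the permissive wording sits in the appendix that sites are told to use when a liver case arises. Section 6.1 sends them to the same appendix for specific liver abnormalities.

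Safety and tolerability is the first-listed objective, and Section 1.4 promises close monitoring, especially for liver toxicity. Expedited evaluation by the sponsor starts from the SAE report (Section 5.5.5), and Section 10.1 describes DSMB input partly in terms of SAE reviews. If a site exercises the option not to report, the 24-hour notice is lost and the case falls out of the serious TEAE summaries in SAP Section 6.5.1. Appendix 12.5 itself puts the rate of bad outcomes under Hy's Law at 10 to 50% (death or transplant), so these are the cases where a clear rule matters most.

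**Working it through.** The documents give no figure on this point, so the check is a comparison of the texts, followed by the weight of a single case.

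**1. Where the two rules overlap**

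| Confirmed finding, no other cause | Section 5.5.1.2 | Appendix 12.5 |
|---|---|---|
| ALT/AST > 3×ULN and TBL > 2×ULN | always reported | may be reported |
| ALT/AST > 8×ULN | not clearly covered | may be reported |
| ALT/AST > 5×ULN lasting over 2 weeks | not clearly covered | may be reported |
| ALT/AST > 3×ULN and INR > 1.5 | not clearly covered | may be reported |
| ALT/AST > 3×ULN with listed symptoms, rash or eosinophilia | not clearly covered | may be reported |

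The contradiction is certain in the first row only. In the other four, Section 5.5.1.2 is tied to a bilirubin rise and the appendix criteria are not, so the permissive wording does not clearly conflict with anything.

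**2. Whether another provision already forces an SAE report in the first row**

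- Sponsor notice (Appendix 12.5): worded as *should*, with no time limit, and limited to cases the site judges possibly attributable to study drug.
- LA-CRF (Appendix 12.5): data capture, with no stated reporting clock.
- Abnormal laboratory findings (Section 5.5.1.1): a clinically significant result not related to underlying disease is reported as an AE or an SAE. This secures an AE record but does not settle seriousness.
- SAE definition (Section 5.5.2): a case that causes death, hospitalization or another listed outcome is serious anyway. The conflict therefore matters for cases whose only route to seriousness is the important-medical-event category.
- Sponsor's list of always-serious events (Section 5.5.2.1): operates once an AE has been reported, and its contents are not given.

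None of these imposes a 24-hour SAE report on a combined case that a site has treated as optional.

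**3. Weight of one case**

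Inputs: about 30 subjects planned (Section 7.1), at least 25 evaluable (Section 2.2.1), and a target minimum of 5 per age cohort (Section 7.1). The shift in the percentage of subjects with a serious TEAE from one reclassified subject is 1/n:

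- n = 30: 1/30 = 3.3 points
- n = 25: 1/25 = 4.0 points
- n = 5: 1/5 = 20 points

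These are maxima. The percentage moves only if the subject has no other serious TEAE, and Section 1.2 reports SAEs in about half of the phase 1 paediatric subjects. The count of serious TEAEs moves by one in any case.

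**The case against.** The strongest reply is that no such case would vanish. The appendix asks that the sponsor be told of severe cases possibly attributable to study drug, calls for an LA-CRF, and sits beside Section 5.5.1.1, which requires an AE or SAE report. Section 5.5.2 lets the sponsor as well as the investigator judge seriousness. SAP Section 6.5.3 tabulates ALT or AST above 3×ULN with bilirubin above 2×ULN whatever the SAE classification, and adds an eDISH plot. Section 10.1 says the DSMB charter will mandate review of all relevant data.

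Much of this stands. A reader might infer that serious liver cases can go unreported altogether. The documents do not support that: what can be lost or delayed is the SAE classification and its 24-hour report. Whether DSMB review would be delayed depends on a charter that is not among the documents.

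The SAP liver table is a partial backstop. It serves the final analysis, not real-time oversight, and it assumes central-laboratory values, whereas Protocol Section 5.4.2 and Table 1 assign safety samples to the local laboratory.

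A reader might also infer that SAE counts will differ between sites. With about 30 centers for about 30 subjects, roughly one each, such a difference could not be told from chance. The text supports only that like cases could be classified inconsistently.

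Nor does the phase 1 withdrawal for raised liver enzymes (1 of 27 subjects, Section 1.2) show how often the conflict would arise. The documents do not say whether bilirubin rose in that subject, whether a severe criterion was met, or whether the event was reported as an SAE.

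**Conclusion.** The inconsistency is real, is in current text, and should be corrected. It is certain for confirmed ALT/AST above 3×ULN with bilirubin above 2×ULN and no other cause. It would be too strong to say that the appendix contradicts Section 5.5.1.2 for every severe liver abnormality, because the four further criteria need no bilirubin rise. Their problem is a different one: no clear mandatory or optional status relative to Section 5.5.1.2.

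The consequence is possible omission from 24-hour SAE reporting and from the serious TEAE tables, worth up to 3.3 points per case at 30 subjects. This assumes that a site follows the appendix wording, that the case is not serious on another criterion, and, for the percentage, that the subject has no other serious TEAE. The documents give no basis for estimating how many such cases will occur.

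**What to change.** Reconcile Section 5.5.1.2 and Appendix 12.5 so that a single reporting rule applies to combined AST/ALT and bilirubin cases. One way is to state in the appendix that cases falling within Section 5.5.1.2 are reported as that section requires.

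A bare cross-reference in place of the permissive sentence would not be enough. It would remove the only liver-specific SAE wording for the four severe criteria without a bilirubin rise (above 8×ULN; above 5×ULN for over 2 weeks; above 3×ULN with INR above 1.5; above 3×ULN with symptoms). The revised text should say explicitly which reporting rule applies to those, and should keep the sponsor-notification sentence.

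The cost is a sentence or two in the next amendment, since Section 12.1.3 requires changes after approval to be documented as amendments. Design, visits and analyses are unaffected.

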12.6 Common Serious Adverse Events

For this protocol, there is no list of common SAEs anticipated for the study population for the purposes of IND safety reporting.

12.7 Oral Dosing Acceptability Assessment

SITE NUMBER: _____
SUBJECT NUMBER: _____

DATE: ____ / ____ / ____ (DD/MMM/YYYY)

General Instructions

The questionnaire will be completed for all subjects who received oral study medication:

- By the patient him/herself (when the patient is able to do so), or
- By the parent/legal guardian/study nurse (based on input from the patient).

The questionnaire will be completed:

- Following the first oral dose (shortly after taking the study medication).

[figure not shown]
Subject Instructions

You have just taken the oral study medication.

[figure not shown]
- Please answer the three questions below.
- Put a cross in the box below the best answer.
- If you make a mistake, cross it out with a single line and cross the correct answer.
The original entry should still be legible.

Questions

1. How was the TASTE of the medication?

2. How was it to SWALLOW the medication?

SITE NUMBER: _____

DATE: _____ (DD/MMM/YYYY)

SUBJECT NUMBER: _____

3. How would you FEEL if you took the medication again?				
0	1	2	3	4
				
Really bad	Bad	Not bad, not good	Good	Really good
				

13 ATTACHMENT 1: SUBSTANTIAL AMENDMENT 3

I. The purpose of this amendment is:

Substantial Changes
1. Clarify Vital Signs for Subjects who Receive Oral Dosing
DESCRIPTION OF CHANGE: Additional text is added to specify that no additional vital signs are needed on dosing days for oral administration other than screening and end of treatment.
RATIONALE: This change is made to clarify that no additional vital signs are required for subjects who receive oral dosing as the additional vital signs are only required for monitoring of the intravenous dosing.
2. Clarify Pregnancy Testing in the Schedule of Assessments
DESCRIPTION OF CHANGE: Additional text is added to footnote 12 (Table 1) to clarify that the pregnancy test may be either urine or serum.
RATIONALE: Added text to clarify the type of pregnancy test that is acceptable.
3. Update Timing of the Return Visit
DESCRIPTION OF CHANGE: Text is added to specify that the return visit should occur on days when study-related assessments are required.
RATIONALE: Added text to clarify the timing of return study visits to minimize the burden to subjects for unnecessary return visits.
4. Change Age Requirement for Oral Formulation
DESCRIPTION OF CHANGE: The lower limit on the age requirement for oral dosing is changed from “12 years of age” to “6 years of age and with a body weight of at least 12 kg.” The dose rationale is updated with additional data from Part 2 of Study 9766-CL-0046 (6 to < 11 years of age) to support this change.
RATIONALE: Added lower age range and minimum body weight for oral dosing as supported by additional

pharmacokinetic modeling data provided.

5. Add Investigator Guidance for Successful Outcome

DESCRIPTION OF CHANGE:

A table is added to provide guidance to the investigator defining the elements of a successful outcome.

RATIONALE:

Added guidance for the investigator regarding the definition of a successful outcome to aid in their decision making regarding end of treatment.

6. Update Inclusion Criterion #2

DESCRIPTION OF CHANGE:

This criterion is updated to extend the timing of diagnostic tests to confirm invasive fungal disease to 10 calendar days after the first dose of study drug.

RATIONALE:

Revised the timeframe allowed to confirm invasive fungal infection diagnosis to align with time estimated per site's institutional practice.

7. Update Inclusion Criterion #3

DESCRIPTION OF CHANGE:

This criterion is updated to clarify that the administration will be intravenous and to specify that the subject must be able to swallow oral capsules.

RATIONALE:

Added clarification that subject must either have venous access for intravenous infusion or the ability to swallow oral capsules to be eligible for the study.

8. Update Exclusion Criterion #7

DESCRIPTION OF CHANGE:

This criterion is updated to include allergy, hypersensitivity or serious reaction to "any component of the study drug formulation."

RATIONALE:

Updated the exclusion criterion to include allergy or hypersensitivity to ensure subject safety.

9. Add Discontinuation Due to Serious Hypersensitivity Adverse Reactions

DESCRIPTION OF CHANGE:

Text is added to state that subjects who develop serious hypersensitivity adverse reactions without alternative etiology will be discontinued from treatment.

RATIONALE:

Added discontinuation criterion for serious hypersensitivity adverse reactions as an additional safety precaution.

Nonsubstantial Changes

1. Update Contact Details of Key Sponsor's Personnel

DESCRIPTION OF CHANGE:

The Astellas medical monitor is replaced.

RATIONALE:

Sponsor personnel details are updated based on changes to study team members.

2. Update Inclusion Criterion #8

DESCRIPTION OF CHANGE:

The phrase “of childbearing potential” is removed from this criterion.

RATIONALE:

This change is made to correct an error.

3. Add Appendix with Acceptability Assessment

DESCRIPTION OF CHANGE:

The Acceptability Assessment is added to the protocol as Appendix 12.7. Cross references to this appendix are added as appropriate.

RATIONALE:

This change is made to include the details of the Acceptability Assessment to be used for this study.

4. Update Packaging of Oral Capsules

DESCRIPTION OF CHANGE:

The packaging information for oral capsules is updated to specify that aluminum blisters with desiccants will be used, and then placed in secondary child-resistant cards.

RATIONALE:

Added additional details related to the packaging of oral capsule for packaging identification purposes.

5. Update Treatment Compliance
 
DESCRIPTION OF CHANGE: Additional details are added to the treatment compliance section.

RATIONALE: Provided additional details regarding treatment compliance for oral dosing to ensure appropriate subject compliance and re-education throughout the study.

6. Clarify that Members of the Data and Safety Monitoring Board (DSMB) could be Members of the Adjudication Committee (AC), and Vice Versa
 
DESCRIPTION OF CHANGE: Section 10.1 is updated to clarify that members of the DSMB could be members of the AC, and Section 10.2 is updated to clarify that members of the AC could be members of the DSMB.

RATIONALE: This change is made to clarify that members may belong to both groups.

7. Minor Administrative-type Changes
 
DESCRIPTION OF CHANGE: Include minor administrative-type changes (e.g., typos, format, numbering and consistency throughout the protocol).

RATIONALE: To provide clarifications to the protocol and to ensure complete understanding of study procedures.

II. Amendment Summary of Changes:

IIA. Substantial Changes

IV Synopsis, Dose(s)
WAS: The investigator may determine the appropriate route of administration for each subject. They can change dosing between the 2 routes of administration (intravenous ⇄ oral) throughout the treatment period as needed.
IS AMENDED TO: The investigator may determine the appropriate route of administration for each subject. The investigator can switch They can change dosing between the 2 routes of administration (intravenous ⇄ oral) throughout the treatment period as needed. Changes to route of administration will be documented.

V Flow Chart and Schedule of Assessments

Table 1 Schedule of Assessments (IA and IM Subjects) – Screening through Day 84 and IA Follow-up (30 and 60 Days Post-Day 84 or EOT [Last Dose of Study Drug])

WAS:
3. Diagnosis must be completed within 7 days of first dose. 5. Vital signs are to be measured within 1 hour prior to and approximately 1 hour after the end of each infusion. 9. For both intravenous and oral dosing: 24-hour pharmacokinetic samples will be obtained on any day between day 14 and day 42, while the subject is still receiving study drug, for subjects who consent to participation in the 24-hour pharmacokinetic assessment. 12. Pregnancy testing not applicable for male subjects. Not necessary for female subjects who are of non-childbearing potential (e.g., premenarchal in the judgment of the investigator on day 1 and throughout the study treatment, or documented surgically sterile). 15. For both intravenous and oral dosing: Loading doses on days 1 and 2 will be administered every 8 (\pm 2) hours. The first maintenance dose should start 12 to 24 hours after the administration of the last loading dose. Subsequent maintenance doses will be administered once daily (24 \pm 2 hours from the previous maintenance dose). Subjects who are discharged from the hospital with oral capsules for at-home administration must return weekly to receive new oral dosing supplies.
IS AMENDED TO:
3. Diagnosis must be completed within 107 days of first dose. 5. Vital signs are to be measured within 1 hour prior to and approximately 1 hour after the end of each infusion. No additional vital signs are needed on dosing days for oral administration. 9. For both intravenous and oral dosing: 24-hour pharmacokinetic samples will be

obtained on any **one** day between day 14 and day 42, while the subject is still receiving study drug, for subjects who consent to participation in the 24-hour pharmacokinetic assessment.

12. Pregnancy testing not applicable for male subjects. Not necessary for female subjects who are of non-childbearing potential (e.g., premenarchal in the judgment of the investigator on day 1 and throughout the study treatment, or documented surgically sterile). **Pregnancy testing may be urine or serum, dependent upon institutional standard of care.**

15. For both intravenous and oral dosing: Loading doses on days 1 and 2 will be administered every 8 (\pm 2) hours. The first maintenance dose should start 12 to 24 hours after the administration of the last loading dose. Subsequent maintenance doses will be administered once daily (24 \pm 2 hours from the previous maintenance dose). Subjects who are discharged from the hospital with oral capsules for at-home administration must return weekly to receive new oral dosing supplies. **Return visits should coincide with days when study-related assessments are required. Oral dosing is allowed for 6 to < 18 years of age and with a body weight of at least 12 kg.**

V Flow Chart and Schedule of Assessments

Table 2 Extended Schedule of Assessments (IM Subjects) – Day 85 through Day 180 and IM Follow-up (30 and 60 days Post-Day 180 [Last Dose of Study Drug])

WAS:

Period	
Day	85
Visit window (days)	

3. Vital signs are to be measured within 1 hour prior to and approximately 1 hour after the end of each infusion.

10. For both intravenous and oral dosing: Subsequent maintenance doses will be administered once daily (24 \pm 2 hours from the previous maintenance dose). Subjects who are discharged from the hospital with oral capsules for at-home administration must return weekly to receive new oral dosing supplies.

IS AMENDED TO:

Period	
Day	85
Visit window (days)	\pm 2

3. Vital signs are to be measured within 1 hour prior to and approximately 1 hour after the end of each infusion. **No additional vital signs are needed on dosing days for oral administration.**

10. For both intravenous and oral dosing: Subsequent maintenance doses will be administered once daily (24 \pm 2 hours from the previous maintenance dose). Subjects who are discharged from the hospital with oral capsules for at-home administration must return weekly to receive new oral dosing supplies. **Return visits should coincide with days when study-related assessments are required. Oral dosing is allowed for subjects 6 to < 18 years of age and with a body weight of at least 12 kg.**

IV Synopsis, Study Design Overview and 2 Study Objective(s), Design and Endpoints

